3.7.4 Additional Efficacy Endpoints

The 11 additional efficacy endpoints are just the key secondary endpoints measured at one and two years following the final islet transplant (the key secondary endpoints are measured at one and two years after the initial transplant). They will be analyzed in exactly the same way as the key secondary endpoints but no adjustment will be made for multiple comparisons.

3.7.5 Analysis at 75 ±5 Days Following the Initial and Final Infusion(s)

The analysis will be conducted for the ITT population at 75±5 days after the initial islet infusion. Separate analyses will be conducted for each variable observed at 75±5 days after the initial islet infusion and at 75±5 days after the final islet infusion. These times can differ by as much as 8 months for individual islet recipients.

3.7.5.1 Analysis templates

Two analytic templates are described as follows:

- 1) **Binary outcome variables:** For a binary variable, we will calculate the sample proportion based on the pooled sample as the point estimate of the true rate. The exact binomial 95% confidence interval is constructed for the true rate.
- 2) **Continuous scale outcome variables:** For a continuous variable, the sample mean \bar{x} and sample standard deviation s_x are calculated based on the pooled sample. The sample mean \bar{x} is used as a point estimate of the true mean μ . The Shapiro-Wilk test will be used to test the normality of this continuous variable. If the hypothesis of normally distributed data is not rejected at the 0.05 significance level, the usual

normal 95% confidence interval $\bar{x} \pm t_{0.025}^{n-1} \times \frac{s_x}{\sqrt{n}}$ is constructed for the true mean μ . If

the data are not normally distributed, the transformations $y = f(x) = \log x$, \sqrt{x} and $1/x$ of this variable will be examined sequentially until we fail to reject the hypothesis of normality using the Shapiro-Wilk test at the 0.05 significance level. If a transformation f is identified such that normality holds (*i.e.*, *normality acceptable for the transformed data $y=f(x)$*), then the sample mean \bar{y} and sample standard deviation s_y are calculated for the transformed variable. The 95% confidence interval will be constructed as

$$\left[f^{-1} \left(\bar{y} - t_{0.025}^{(n-2)} \frac{s_y}{\sqrt{n}} \right), f^{-1} \left(\bar{y} + t_{0.025}^{(n-2)} \frac{s_y}{\sqrt{n}} \right) \right]$$

If these transformations fail to achieve normality, the bootstrap will be adopted. 1000 bootstrap samples sampled from the original data set *with replacement are obtained*. For each bootstrap sample, the sample mean is calculated and then the 2.5 and 97.5 percentiles, $p_{0.025}$ and $p_{0.975}$, will be identified from the 1000 bootstrap sample means.

The interval $[p_{0.025}, p_{0.975}]$ will reported as the bootstrap 95% confidence interval for the true mean.

Analysis template tables for the following efficacy endpoints at 75±5 days following the initial and final infusion are provided in SAP Appendix 9.

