3.7.5.5 Glycemic lability index

LI is a measure of lability which is based on the change in glucose over time. The LI requires 4 or more daily capillary blood glucose (BG) measurements over a 4 week period. For each week, the sum of the squared differences in consecutive glucose readings is divided by the hours apart the readings are determined. Only differences in time that were greater than or equal to 1 hour and less than or equal to 12 hours are used in calculations. This sum is calculated for each of the four weeks and the LI is the mean of the four weekly values [3], that is:

$$LI = \frac{1}{4} \times \sum_{i=1}^4 \sum_{j=1}^{N_i} \frac{(\Delta Gluc_{i,j})^2}{\Delta h_{i,j}}$$

where $\Delta Gluc_{i,j}$ is the j^{th} eligible difference of glucose readings in the i^{th} week, $\Delta h_{i,j}$ is the time interval in hours for the j^{th} eligible difference of glucose readings in the i^{th} week.

N_i is the total number of the eligible differences of glucose readings in the i^{th} week which may vary from week to week.

Most subjects have scores under 300 mmol/L²/h·wk⁻¹ with a median of 223 (25 – 75th percentiles 130 – 329 mmol/ L²/h·wk⁻¹). An LI ≥ 433 mmol/ L²/h·wk⁻¹ (90th percentile) indicates serious problems with glycemic lability. The LI will be measured at 75 ± 5 days following the initial and final infusion (if applicable). The first analysis for this variable directly uses LI and adopts the method described for continuous scale variables. Change from baseline will also be computed and analyzed using the same methods.

Subjects will also be categorized into two groups depending on whether or not the LI ≥ 433 mmol/ L²/h·wk⁻¹. The analysis of the rate of serious problems with glycemic lability will also be analyzed using the method for binary outcomes.

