3.9.4.1 Analysis for SF-36 survey

3.9.4.1.1 *Analysis at 75 ± 5 days following the initial and final islet transplant*

We will compute the Summary Physical Component (SPC) and Summary Mental Component (SMC) from the version 2 SF-36 health survey form at 75 ± 5 days following the initial and final islet transplant (if applicable). For both SPC and SMC, we will calculate the sample mean and construct the 95% confidence interval of the mean value using the method for a continuous variable described in SAP section 3.6.3. We will also compute the change from baseline for both scores and analyze the changes using the same method.

3.9.4.1.2 *Analysis at 365 ± 14 days following the initial and final islet transplant*

Obtain the SPC and SMC scores from the version 2 SF-36 health survey form at 365 ± 14 days following the initial and final islet transplant (if applicable).

For both SPC and SMC, we calculate the sample mean and construct the 95% confidence interval of the mean value using the method for a continuous variable described in SAP Section 3.6.3.

3.9.4.1.3 *Comparison of SPC and SMC at three time points*

For each subject, we will obtain his/her score at baseline, 75 ± 5 and 365 ± 14 days following the initial islet transplant. The analysis adopts the method of linear mixed models with a term for time (baseline, 75 days following the initial islet transplant and 365 days following the initial islet transplant) and repeated measures on subjects.

The analysis proceeds as follows:

The Shapiro-Wilk test is applied to test the hypothesis that the QOL score is normally distributed. If the normality hypothesis is not rejected at significance level 0.05, a linear mixed model analysis will be performed to test whether the mean QOL score is the same among the three time points. This model will include a term for time (baseline, 75 days, and 365 days) with repeated measurements on subjects.

The results would be treated as follows:

- 1) If the p-value is greater than 0.05, we conclude there is no evidence to claim the difference of the QOL score from the baseline.

- 2) If the p-value is less than 0.05, we would compute the overall 95% confidence intervals for the pair-wise differences in the QOL score between any two time points using the Bonferroni adjustment for multiple tests.

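### When the transform branch of the continuous-variable recipe is used, the SAP prints an arithmetic mean beside a confidence interval for a different quantity, with the wrong degrees of freedom.

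*SAP*

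**What the plan says.** SAP section 3.7.5.1 gives one template for continuous variables, and section 3.6.3 gives the same recipe for baseline data.

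- **Estimate.** In section 3.7.5.1 the raw sample mean "is used as a point estimate of the true mean", whichever branch is later used.
- **Raw branch.** If Shapiro-Wilk does not reject at 0.05, a t interval on n-1 degrees of freedom is built for the true mean.
- **Transform branch.** Otherwise log x, √x and 1/x "of this variable will be examined sequentially until we fail to reject the hypothesis of normality using the Shapiro-Wilk test". The mean and SD "are calculated for the transformed variable. The 95% confidence interval will be constructed as" the inverse transform of ȳ ± t·s_y/√n, with t on n-2 degrees of freedom.
- **Bootstrap branch.** "If these transformations fail to achieve normality, the bootstrap will be adopted", and its percentile limits "will reported as the bootstrap 95% confidence interval for the true mean".

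Appendices 9 and 10 have one row label for every continuous outcome, the 95% CI of the mean, with columns for each center and the total. Section 3.9.4.1 sends QOL scores to the same recipe, to "construct the 95% confidence interval of the mean value using the method for a continuous variable". Several change scores go there too; for the lability index (LI), section 3.7.5.5 says "Change from baseline will also be computed and analyzed using the same methods".

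**The concern.** Inverting the limits for the mean of f(x) gives limits for f⁻¹ of that mean. For the log this is the geometric mean, for the square root the squared mean root, and for the reciprocal the harmonic mean. For positive data that vary at all, each lies below the arithmetic mean. The transform-branch sentence names no other target, while the other two branches are both stated to be for the true mean and the table rows say the same. A reader of the final tables would therefore take the interval as the uncertainty of the printed mean.

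These secondary analyses are descriptive, so the estimate and its interval are the whole result. A skewed variable could show a mean outside its own interval. One variable could also be left raw at day 75 and transformed at day 365, so that its intervals describe different quantities.

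**Working it through.** **The plan's own figure.** The only stated figure is the nominal 95%. The log-branch interval does reach it, but for the geometric mean: simulated coverage at n=48 is 0.95, 0.95 and 0.94 for log-normal data with log-SD 0.518, 0.688 and 1.0.

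**Inputs.** n = 48 (section 2.1). Section 3.7.5.5 describes LI ("Most subjects have scores under 300") with median 223, quartiles 130 and 329, and 90th percentile 433. Assumption: these percentiles apply to the trial population. The shape is not given, so several are tried.

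**Log-SD implied by the percentiles.**
- Both quartiles: ln(329/130)/1.349 = 0.688
- 25th percentile alone: ln(223/130)/0.6745 = 0.80
- 75th percentile alone: ln(329/223)/0.6745 = 0.58
- 90th percentile: ln(433/223)/1.2816 = 0.52

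A log-normal shape would give one value. On the square-root scale the three single percentiles give SDs of 5.2, 4.8 and 4.6, which agree better.

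**Typical log-branch interval at n = 48**, with t(46) = 2.013:
- Log-SD 0.688: true mean 223·exp(0.688²/2) = 283. Half-width 2.013·0.688/√48 = 0.200, so the limits are 223·exp(±0.200) = 183 to 272. The mean lies above the upper limit.
- Log-SD 0.518: true mean 223·exp(0.518²/2) = 255. Half-width 0.151, so the limits are 192 to 259. The mean is just inside.

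Under a square-root-normal shape the interval targets 223, while the true mean is 223 + SD², or 244 to 250 for SD 4.6 to 5.2.

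**Whole recipe simulated** (Shapiro-Wilk, the three transforms with t(n-2), then bootstrap; 4,000 data sets per scenario; ranges are across repeated runs):

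| Shape | Coverage of true mean, n=48 | Coverage, n=24 | Sample mean outside its interval, n=48 |
|---|---|---|---|
| Log-normal, log-SD 0.688 | 0.38–0.39 | 0.67 | over 80% |
| Log-normal, log-SD 0.518 | 0.60–0.62 | 0.81–0.82 | about 10% |
| Square-root-normal, SD 4.6–5.2 | 0.74–0.79 | 0.85–0.88 | 10–16% |
| Log-normal, log-SD 0.1 to 0.2 (illustrative mild skew) | 0.92–0.95 | 0.93–0.95 | none seen |

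In the first row about 95% of data sets took the log branch. Coverage falls as n grows, because Shapiro-Wilk rejects more often and the interval narrows around the wrong target.

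**Degrees of freedom.** A one-sample mean has n-1, as the raw branch uses. At n=48, t(46)/t(47) = 2.0129/2.0117 = 1.0006, or 0.06% wider. At n=6, the size planned for four centers, t(4)/t(5) = 2.776/2.571 = 1.08, or 8% wider.

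**Reciprocal.** 1/x is decreasing for positive x, so the inverse of the lower transformed limit is the larger number and the printed pair is reversed.

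**Undefined transforms.** Log and 1/x fail at zero (the β-score and Clarke score start at 0). Log and square root fail for negative values, which change scores can take. The SAP gives no rule for this. If an uncomputable transform is read as failed, the bootstrap takes over; for a skewed change score with both signs, simulated coverage at n=48 was then 0.94.

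**The case against.** The strongest counter-argument is that little depends on these intervals. Section 3.7.2 calls the secondary analyses descriptive and not intended for the efficacy decision. The primary and key secondary endpoints are binary with exact binomial methods, and the three-time-point QOL comparison goes straight from a normality rejection to a bootstrap. That stands, and it limits the severity.

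Three stronger readings are tempting and not supported:

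- **That every continuous interval is wrong.** The recipe reaches every continuous variable, but the fault appears only when Shapiro-Wilk rejects and a transform then passes. Mildly skewed variables keep near-nominal coverage.
- **That coverage is below 40%.** This comes from a log-normal shape with log-SD 0.688. That model puts the 90th percentile at 223·exp(1.2816·0.688) = 539, whereas the SAP gives 433. Milder shapes that fit the percentiles at least as well give 0.60 to 0.79. The percentiles are also a general description of scores, not post-transplant data.
- **That intervals for change scores and percent reductions miss their target.** The text leaves a step unspecified; it does not force a wrong interval, since the bootstrap fallback targets the raw mean.

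It is also fair that the transform-branch sentence does not itself say true mean. The target is inferred from the point estimate, the two neighbouring branches and the table label, and nothing in the SAP points elsewhere. The reversed limits and the n-2 are small: the 1/x branch was taken in about 2% or fewer of the LI-scaled data sets, and the 8% applies only to a six-subject center that enters the branch. Both are still errors in a stated formula.

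**Conclusion.** The point holds as a correction to the descriptive tables. In the transform branch the interval belongs to a geometric, squared-mean-root or harmonic mean while the estimate and row label are for the arithmetic mean. That mismatch, the n-2 and the reversed 1/x limits follow from the formulas without any distributional assumption.

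The size does depend on assumptions. With the SAP's LI percentiles taken to apply to the trial population and n=48, coverage of the true mean is about 0.4 to 0.8 across the shapes tried, against a nominal 0.95. For mildly skewed variables there is little loss. Exposed are the continuous baseline, secondary efficacy and single-time-point QOL intervals. The lack of a rule for zero or negative values is a gap to close, not a demonstrated coverage failure. No efficacy conclusion rests on these intervals.

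**What to change.** In sections 3.6.3 and 3.7.5.1, choose one of two routes.

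1. When Shapiro-Wilk rejects, go straight to the percentile bootstrap interval for the mean that the SAP already specifies. Estimate, interval and label then agree at every time point.
2. Keep the transforms only for strictly positive variables, use t on n-1 degrees of freedom, print the limits in ascending order, and report the matching back-transformed estimate (for example the geometric mean). Change the row label in Appendices 9 and 10 to name that quantity, and fix the scale per variable so that all time points are comparable.

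Under either route, state that change and percent-change scores are not transformed.

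The cost is SAP wording and a small program change; no data, subjects or sample size are involved. The downside of the first route is that intervals for the mean of strongly skewed data fall somewhat short of 95%: at n=48 the bootstrap and the plain t interval cover about 0.90 to 0.94 for log-normal data with log-SD from 1.0 down to 0.518. The second route covers its own target at about 0.94 to 0.95 but no longer describes the arithmetic mean.

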observe a rate larger than 70%. With a sample size of 48 transplanted subjects, 31 subjects (65%) would need to achieve a favorable outcome for the exact 95% lower confidence bound to rule out a 50% or lower true rate. (This result is not shown in the table; 65% favorable outcome rate of 48 subjects transplanted results in 31 successfully transplanted subjects). The proposed sample size is 48 subjects. Each participating center is expected to enroll at least 6 subjects.

Table 3 displays the probability that the study would conclude that the true favorable outcome rate is at least 50% for several selected values of the true favorable outcome rate. The tabulated probabilities are the power that a one-sided binomial test of the null hypothesis $H_0: p < 0.5$ versus the alternative hypothesis $H_a: p \geq 0.5$ would conclude that the true favorable outcome rate is at least 50% given that the selected value is the true underlying favorable outcome rate. These values are obtained by calculating the binomial probability that at least 31 out of 48 total enrolled subjects would achieve the favorable outcome given the true outcome rate.

Table 3- The power to rule out a favorable outcome rate that is less than or equal to 50% for the given true favorable outcome rate.

True Favorable Outcome Rate	Power to Rule Out Favorable Outcome Rate
10%	0.0000
20%	0.0000
30%	0.0000
40%	0.0005
50%	0.0297
60%	0.3111
70%	0.8359
80%	0.9962
90%	1.0000

This table shows that if the true favorable outcome rate is 70%, the power of concluding that the rate is over 50% is 0.8359 for a 5% level test.

3. General Analysis Definitions

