3.6.2 Statistical Analysis of Baseline Data

The number of subjects who do not meet the eligibility criteria will be reported, grouped by center. The numbers will be further broken down by the reasons for exclusion. These numbers and the corresponding rates will be reported in the summary table provided in SAP Appendix 7.

Descriptive statistics of baseline data, grouped by center, will be presented in a summary table. Continuous data will be summarized by mean, standard deviation, median, minimum, and maximum. Categorical data will be presented as numbers and percentages. The template of this table is described in SAP Appendix 1. Since the number of subjects randomized in each center is small, there will be no significance tests for the differences of the baseline data among the seven centers.

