3.6.3 Analysis of Diabetes Control Variables

Diabetic control variables include insulin requirement, fasting and post-prandial plasma glucose and C-peptide, glucose and C-peptide 90 minutes post Boost[®] (or equivalent) glucose challenge, number of hypoglycemic events in the last year, MAGE score, LI,

Clarke score, HYPO score, β -score, and C-peptide/(glucose·creatinine) ratio (the ratio of C-peptide to the product of glucose and creatinine).

The distribution of number of hypoglycemic events in the last year will be presented in tabular form.

The remaining diabetes control variables are all continuous scale variables and will be displayed as mean, standard deviation, median, minimum and maximum. The Shapiro-Wilk test will be used to test the normality of this continuous variable. If the hypothesis of normally distributed data is not rejected at the 0.05 significance level, the usual normal

95% confidence interval $\bar{x} \pm t_{0.025}^{n-1} \times \frac{S_x}{\sqrt{n}}$ will be constructed for the true mean μ . If the data

are not normally distributed, the transformations $y = f(x) = \log x$, \sqrt{x} and $1/x$ of these variables will be examined sequentially until we fail to reject the hypothesis of normality using the Shapiro-Wilk test at the 0.05 significance level. If a transformation is identified such that normality holds then the sample mean \bar{y} and sample standard deviation s_y will be calculated for the transformed variable. The 95% confidence interval will be constructed as

$$\left[f^{-1} \left(\bar{y} - t_{0.025}^{(n-2)} \frac{S_y}{\sqrt{n}} \right), f^{-1} \left(\bar{y} + t_{0.025}^{(n-2)} \frac{S_y}{\sqrt{n}} \right) \right].$$

If these transformations fail to achieve normality, the bootstrap method will be adopted. One thousand bootstrap samples from the original data set with replacement are obtained. For each bootstrap sample, the sample mean is calculated. The 2.5 and 97.5 percentiles, $p_{0.025}$ and $p_{0.975}$, will be identified from the 1000 bootstrap sample means. The interval $[p_{0.025}, p_{0.975}]$ will be reported as the bootstrap 95% confidence interval for the true mean.

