Suppose there are k centers and each center recruits n_i subjects, $i=1, \dots, k$: it is anticipated that $k=6$ and $(n_1, n_2, n_3, n_4, n_5, n_6) = (12, 12, 6, 6, 6, 6)$. Let y_i denote the observed number of favorable outcomes at center i out of n_i subjects, and let p_i denote the true underlying success probability at the i th center. The random-effects framework postulates that the observed number of successes for each center, y_i , conditional on p_i , is a draw from a binomial distribution, independently at each center:

$$y_i | p_i \text{ is Binomial}(n_i, p_i)$$

for $i=1, \dots, k$. Further denote the log odds of success at each center by θ_i

$$\theta_i = \log[p_i/(1-p_i)]$$

for $i=1, \dots, k$. Furthermore, assume that there may be between-center variability, but all centers are exchangeable: let θ_i given μ and σ^2 be like a sample from a normal population:

$$\theta_i | \mu, \sigma^2 \text{ is } N(\mu, \sigma^2).$$

The values μ and σ represent the population log odds and population between-center standard deviation of the log-odds respectively.

Let $\pi = e^\mu / (1 + e^\mu)$, the inverse log odds transformation, then π is the population probability of favorable outcome, the underlying predicted success probability for the population of centers.

A Bayesian approach, using Monte Carlo Markov Chain (MCMC) methods, will be implemented to estimate parameters and hyperparameters. The parameters of direct

interest are: the overall probability of favorable outcome π , and each of the probabilities of favorable outcome at individual centers p_i , $i=1, \dots, k$.

3.7.2.1.2 *The prior distribution*

The analysis of the CIT-07 data uses a very vague prior distribution with the distribution of μ assumed uniform and the distribution of σ^{-2} , denoted as τ , assumed to have an independent and proper gamma distribution with a large standard deviation. Specifically, τ has a density proportional to $\tau^{\alpha-1} e^{-\beta\tau}$ for $\tau > 0$ [18, p. 39]: values of $\alpha=2$ and $\beta=1.5$ are specified for analysis. These values lead to stable estimation and are consistent with having very little prior information on the between center variability [19]. The location of the prior mean of the precision is also approximately consistent with historical data and the variance has been inflated to represent uncertainty.

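### Intervals for transformed means use n-2 instead of n-1 degrees of freedom, and the table shells ask for center-level intervals although the percentile bootstrap fallback is too narrow at six subjects

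*SAP*

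**What the plan says.** SAP section 3.7.5.1 sets a three-step rule for continuous endpoints. If Shapiro-Wilk does not reject normality, the interval for the mean is the usual one, with t on n-1 degrees of freedom. If it rejects, the log, square root and reciprocal transformations "will be examined sequentially until we fail to reject the hypothesis of normality using the Shapiro-Wilk test at the 0.05 significance level". The interval is then built on the transformed scale with t on n-2 degrees of freedom and standard error s_y/√n, and is back-transformed. If none passes: "If these transformations fail to achieve normality, the bootstrap will be adopted". The limits are the 2.5 and 97.5 percentiles, which "will be identified from the 1000 bootstrap sample means". Section 3.6.3 gives the same rule for baseline variables, with the same change from n-1 to n-2 and the same last step: "If these transformations fail to achieve normality, the bootstrap method will be adopted".

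On the sample, section 3.7.5.1 says that the mean and standard deviation "are calculated based on the pooled sample". Section 2.4 gives its planned size: "The proposed sample size is 48 subjects". Section 3.7.5.1 refers to Appendix 9 for its tables. Appendices 9 and 10 list a 95% interval for the mean under each continuous outcome, in six center columns as well as the Total column. Section 3.7.2.1 anticipates two centers of 12 subjects and four of 6. No other interval method is given for the center columns.

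**The concern.** There are two separate faults.

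First, the degrees of freedom change from n-1 to n-2 between two formulas that estimate the same kind of quantity. Each has one sample, one estimated mean and a standard error of s/√n. Transforming the data before averaging does not use up a further degree of freedom.

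Second, the method text and the table shells do not match. The text describes a pooled analysis of about 48 subjects, while the shells need an interval from 6 or 12. A programmer filling the shells would have only the section 3.7.5.1 rule to apply, and its last step is unsuitable at n=6. Outcomes with many zeros or a ceiling, such as insulin dose or duration of hypoglycemia, are the likeliest to end there, because no transformation removes a spike of tied values and log and reciprocal are undefined at zero. The center columns would then carry a 95% label on intervals that do not deliver it.

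**Working it through.** **Inputs.** Pooled n=48 (section 2.4); center sizes 12 and 6 (section 3.7.2.1); nominal level 95%; 1000 resamples (section 3.7.5.1). The SAP gives no distribution for any continuous endpoint, so every simulated outcome below is an assumption.

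**1. Degrees of freedom.** The width ratio is t(0.975, n-2) / t(0.975, n-1). The actual coverage of the n-2 interval, for data normal on the transformed scale, is 1 − 2·P(t with n-1 df > t(0.975, n-2)).

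| n | t on n-1 | t on n-2 | ratio | coverage with n-2 |
|---|---|---|---|---|
| 6 | 2.571 | 2.776 | 1.080 | 96.1% |
| 12 | 2.201 | 2.228 | 1.012 | 95.2% |
| 48 | 2.0117 | 2.0129 | 1.0006 | 95.01% |

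Using n-1 restores exactly 95% under that assumption.

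**2. Why the percentile bootstrap is narrow at small n.** The resampled means have standard deviation s·√((n−1)/n)/√n, and their 2.5 and 97.5 percentiles lie roughly 1.96 of these from the sample mean. The effective multiplier of s/√n is therefore about 1.96·√((n−1)/n), to be compared with t on n-1.

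- n=6: 1.96·√(5/6) = 1.79 against 2.571, a ratio of 0.70. Implied coverage for normal data is 86.6%.
- n=12: 1.96·√(11/12) = 1.88 against 2.201, a ratio of 0.85. Implied coverage is 91.3%.
- n=48: 1.96·√(47/48) = 1.94 against 2.012, a ratio of 0.96. Implied coverage is 94.2%.

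The shortfall against the t multiplier depends on n, not on the shape of the data. Direct simulation of the percentile bootstrap with normal data agrees: 86% at n=6, 91% at n=12 and 93% at n=48.

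**3. Simulated coverage over all samples, for assumed outcomes.** At n=6: exponential 81%, half zeros with an exponential or lognormal remainder 72 to 76%, lognormal with log-SD 1 75%, and lognormal with log-SD 1.5 62%. At n=12 the range over all outcomes tried was 70 to 91%. At n=48 it was 82 to 94%.

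**4. Coverage only among samples that reach the bootstrap, after the full Shapiro-Wilk and transformation sequence, at n=6.**

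| Assumed outcome | Share reaching the bootstrap | Coverage there |
|---|---|---|
| Positive skewed (exponential, gamma, lognormal) | 0.3 to 0.5% | 49 to 66% |
| Zero-inflated (30 to 70% zeros) | 13 to 81% | 56 to 63% |
| Ceiling | 71% | 75% |
| t on 3 df | 8% | 80% |
| Outlier mixture | not quoted here | 89% |

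So the range is roughly 50 to 90%. At n=48 the same conditional coverage was mostly 89 to 95%; its extremes were about 77% (lognormal with log-SD 1.5, reached in about 5% of samples) and 97%.

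**The case against.** The strongest reply is that section 3.7.5.1 is written for the pooled sample, where the degrees-of-freedom slip changes the width by 0.06% and the percentile bootstrap is close to nominal for most outcomes. That stands, and it moves the second fault to the shells. They ask for intervals at sizes for which the text was not written.

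It is also fair that the bootstrap is not the only cause of poor coverage at n=6. An ordinary t interval on n-1 degrees of freedom also falls short on such data: in simulation over all samples it covered 89% for exponential data and 82% for half zeros, against 81% and 76% for the bootstrap. This argues for removing the center-level interval rather than exchanging one small-sample method for another.

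Section 3.6.2 should not be pressed too far. "Since the number of subjects randomized in each center is small" is its reason for not testing baseline differences between centers; it does not address intervals. The baseline template in Appendix 1 has no interval row, so only the degrees-of-freedom point applies to section 3.6.3.

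A reader might infer a single coverage figure for the center columns, for example a value in the 60s or 70s. The SAP does not support one: the value depends on the unstated outcome distribution and on whether a sample reaches the bootstrap at all. A reader might also quote the much larger degrees-of-freedom ratios at n=2 to 4 for final-infusion data, but the SAP gives no such sizes. Nor is a different bootstrap shown to be needed in the Total column.

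**Conclusion.** Both faults are real and minor. The n-2 degrees of freedom are wrong as written in sections 3.6.3 and 3.7.5.1, whatever the data. The error is conservative and reaches 8% of width only at n=6. The mismatch between the pooled method and the center columns of Appendices 9 and 10 is the larger fault. At n=6 a percentile bootstrap of the mean covers about 86% in the favorable case of normal data and roughly 50 to 90% in the assumed cases that actually reach it.

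The degrees-of-freedom result and the multiplier argument rest on no endpoint data. The lower coverage figures rest on assumed distributions and on the anticipated center sizes.

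It would be wrong to infer that the pooled secondary results or the efficacy conclusion are unreliable for this reason. Section 3.7.2 declares these analyses descriptive, and the primary endpoint has its own exact binomial interval. Correcting the degrees of freedom also does not settle what the back-transformed limits estimate, which is a separate question.

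**What to change.** 1. In sections 3.6.3 and 3.7.5.1, use t on n-1 degrees of freedom in the transformed-scale formula as well.
2. In Appendices 9 and 10, remove the 95% interval row for continuous outcomes from the center columns. Keep n, mean, SD, median and range there, and keep the interval in the Total column.
3. Add a sentence to section 3.7.5.1 saying that intervals for continuous endpoints are given for the pooled sample only.

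The pooled percentile bootstrap may stay. The cost is a few words, two table shells and small code edits. The one loss is that no center-level interval will be reported for continuous endpoints.
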